1.1 Objectives**1. Primary Objectives:**

- Photographic evaluation with correct identification of pre-treatment images when compared to the 12 week follow up images performed by three independent reviewers.

2. Secondary Objectives:

- Caliper measurements to show statistically significant improvement on treatment area versus control.
- Subject satisfaction rates at 12 week follow up.
- Safety assessment through the collection of Adverse Events.

1.2 Duration of the Investigation

The sponsor anticipates that all subjects can be enrolled within 3 months. If subject participates in all required visits, then the subject's participation in this study may last up to 6 months. It is anticipated that it will take approximately 3 months to analyze the data collected during this study. The total duration of this study is anticipated to last approximately 12 months.

2.0 PROTOCOL**2.1 Protocol Methodology and Analysis****Methodology:**

Subjects are to be enrolled in this clinical study if they are 18 – 55 years old. A maximum of 68 subjects will be enrolled at up to 6 study centers. Subject will attend a screening/pretreatment visit which may be performed on the same day as the treatment visit. Subjects will receive up to 5 treatments with the TempSure® Firm on one flank. The other flank will be left untreated to serve a control. Subject will be required to return for follow-up visits at 6 weeks and at 12 weeks after the subject's final treatment. All subjects will receive a phone call 1 week (1-10 days) post each treatment. An unscheduled visit or phone call may be performed at any time during the study at the subject's request or as deemed necessary by the site Investigator.

Analysis:

Upcoming generations are proving to have an interest in non-ablative aesthetic treatments and will drive demand for innovated products, procedures, and practice design.ⁱ Due to this shift in patient base, practices need to evolve to adapt to the newer generational ideologies. There have been rapid advances in RF technology over the past few years and the nonsurgical treatment using this energy source offers great promise to our aging population.ⁱⁱ Radiofrequency technology for lipolysis needs to be further investigated to optimize treatment parameters for safe and effective non-ablative aesthetic treatments.

Relevance:

Non-invasive fat reduction is a commonly sought out procedure and continues to increase in demand (+3% from 2018 to 2019)³ perhaps due to the fact that, according to the CDC, the prevalence of obesity in the U.S. was 42.4% in 2017-2018⁴. Currently, the treatments available for non-invasive lipolysis include, but not limited to, radiofrequency, cryolipolysis, laser lipolysis, HIFEM, and ultrasound. The limitations of current products on the market include different side effect profiles and modes of administration.

Testability:

The CoolSculpting device has been cleared for used for cold-assisted lipolysis(breakdown of fat) of bra fat, back fat, banana roll, submental area, thigh, abdomen, and flank, or "love handles" in individuals with a Body Mass Index

(BMI) of 30 or less (FDA K160259). The CoolSculpting study utilized the following evaluation methods: ultrasound and caliper measurements, circumferential measurements, 3D quantification of volume reduction, and blinded, independent review of clinical photographs. This particular study will utilize the collection of before and after photography for blinded, independent review of clinical photographs, caliper measurements, satisfaction scores, and safety data to evaluate the safety and efficacy of the treatment.

Compatibility:

Due to such a high prevalence of obesity in the U.S. and the increasing demand for non-invasive lipolysis treatments, there is a need to treat unwanted in its earlier stages to optimize treatment outcomes. As a subject gets older or the condition worsens, their treatment may need to be more aggressive to get their body to respond the same way that a younger subject or less severe case may be able to respond.

Predictive power:

While this study will observe the effects of the handpieces on lipolysis, results could potentially be applied to a variety of body areas and other potential applications. Assuming that there is significant improvement, it would be appropriate to expect results in different areas where other products and devices have significant results alongside reduction of unwanted fat.

2.2 Protocol Study Design

This is a prospective, open-labeled, randomized, multi-center clinical study to collect efficacy data on the TempSure® Firm.

2.3 Subject Selection Criteria

Subjects will meet the criteria described below:

Inclusion Criteria:

- A healthy male or female between the age of 18 – 55 years old.
- Willing to undergo treatments for fat reduction of the flank area (love handle)
- Understands and accepts obligation not to receive any other procedures on the treatment area through the length of the study.
- Understands and accepts the obligation and is logically able to be present for all visits.
- Is willing to comply with all requirements of the study and sign the informed consent document.

Exclusion Criteria:

- Is pregnant or of childbearing potential and not using medically effective birth control, or has been pregnant in the last 3 months, currently breast feeding or planning a pregnancy during the study.
- The subject is currently enrolled in an investigational drug or device trial or has received an investigational drug or been treated with an investigational device within in the area to be treated 6 months prior to entering this study.
- The subject has a cut, wound, or infected skin on the area to be treated.
- The subject is on local, oral, or systemic anesthetic agents.
- The subject has any condition or is in a situation which in the investigators opinion may put the subject at significant risk, may confound study results or may interfere significantly with the subject's participation.
- The subject is currently enrolled in an investigational drug or device trial, or has received an investigational drug or been treated with an investigational device within in the area to be treated 6 months (or at the discretion of the Investigator) prior to entering this study.

Cautionary Criteria:

- The subject has any embedded electronic device that gives or receives a signal, the device should be turned off or removed prior to treatment.
- The subject has an embedded pacemaker or implantable cardioverter defibrillator (ICD), the client's cardiologist must be consulted prior to treatment.

NOTE: This device has not been tested on patients implanted with electronic devices that receive or emit signals, such as: Pacemakers, Implantable Cardiac Defibrillators (ICD), or Cardiac Resynchronization Therapy (CRT) devices.

- If the neutral pad would need to be placed on a subject that has a metal plate, rod, or any metal implant that could conduct heat from the Smart Handpiece or surgical handpiece.
- The subject is allergic to adhesives, such as glues on medical tape, they should be alerted that a rash may occur on the neutral pad site and an over the counter solution may be used to treat the area.
- The subject is allergic to gold, such as the metallic covering of the TempSure handpieces.
- The subject is allergic to corn, such as the corn derivative ingredient in Parker Aquasonic Gel.
- If the subject has an unhealthy expectation of the results – this is not plastic surgery and all subject should be fully informed of the treatment's expected results.
- The subject has nerve insensitivity to heat in the treatment area.
- The subject has severe laxity or sagging that causes redundant folds of tissue or hanging skin in the area to be treated – this treatment will be ineffective.
- The subject has used Accutane (Isotretinoin) six to twelve months prior to treatment, as this can thin the skin and make it brittle.
- Studies of the use of the RF generator on subjects that have any of the following conditions is unknown:
 - Autoimmune Disease
 - Diabetic
 - Herpes Simplex
- Use caution when treating areas that have scars, tattoos, permanent makeup, and permanent brows.

Be sure to list and concomitant medications or procedures permitted before, during and after the trial

Subjects will be recruited for the study through the existing patient database and advertisements.

Subject populations will not be eligible to participate in the study if they are vulnerable populations such as; children, pregnant women, prisoners, institutionalized individuals, and any persons requiring a legally authorized representative as part of the consenting process.

Subject population characteristics that will not be eligible to participate in the study include non-English speaking individuals and people who cannot read or comprehend English. Employees of the Investigator will not be allowed to participate in the study.

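### Implanted signal-emitting devices and loss of heat sensation are only cautions in section 2.3, and the heat caution leaves out the neutral-pad site

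*Combined protocol and SAP*

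**What the plan says.** Section 2.3 has separate inclusion, exclusion and cautionary lists. The two conditions at issue are named only in the cautionary list.

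- **Implants.** For a subject with "any embedded electronic device that gives or receives a signal, the device should be turned off or removed prior to treatment". For a pacemaker or implantable defibrillator, "the client's cardiologist must be consulted prior to treatment". The note that follows states: "This device has not been tested on patients implanted with electronic devices that receive or emit signals", and continues "such as: Pacemakers, Implantable Cardiac Defibrillators (ICD), or Cardiac Resynchronization Therapy (CRT) devices".
- **Heat sensation.** The entry reads, in full, "The subject has nerve insensitivity to heat in the treatment area". No action is given.

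Three other entries in section 2.3 bear on the point. One inclusion criterion is "A healthy male or female between the age of 18 – 55 years old", with no definition of healthy. One exclusion is "The subject is on local, oral, or systemic anesthetic agents". Another excludes a subject who has "any condition or is in a situation which in the investigators opinion may put the subject at significant risk".

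Other sections supply the rest:

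- Section 2.6 places the neutral pad on the back, in an area the investigator chooses.
- Section 2.14 says that the pad site is checked when the subject reports heat there, and warns of burns if the subject does not report it.
- Section 2.7 requires continuous temperature monitoring during treatment and use of the device according to its manual and reference guide.
- Section 4.0 treats adequate pad current capacity as an essential performance requirement.
- Section 6.0 says that labeling will describe the relevant contraindications.
- Section 3.2 describes the procedure as elective.

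**The concern.** A caution that tells staff to switch off a device, or to consult a cardiologist first, is an instruction for treating the subject. It does not keep the subject out. Section 2.3 therefore appears to admit people whom its own note calls untested, to a cosmetic study of a radiofrequency device. Followed literally, it could lead to an implant being deactivated for that purpose.

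The heat caution has a different gap. It covers the flank being treated, but the subject is also exposed under the neutral pad. Part of the protection against a pad burn is that the subject feels the heat and says so. A subject with reduced sensation on the back cannot do that, and no criterion names that site.

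What is at stake is the safety of a small number of participants. No estimate or test is affected.

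**Working it through.** The main check sets the sections side by side. Arithmetic is needed only for the cost of the fix.

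**1. Do the cautions admit these subjects?** Neither condition is named among the exclusions. The actions attached to the implant cautions make sense only if treatment may follow. Section 2.4 has staff verify the inclusion and exclusion criteria and does not mention the cautionary list.

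**2. Which implants get which safeguard?**

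| Implant | Switch off or remove | Cardiologist | Called untested in the note |
|---|---|---|---|
| Pacemaker, ICD | Yes, if the general entry is read literally | Required | Yes |
| CRT device | Yes | Not stated | Yes |
| Other signal-emitting device | Yes | Not stated | Yes |

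The general and cardiac entries can be followed together. CRT devices are named only in the note, so they carry only the general instruction.

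**3. Does anything cover sensation at the pad site?**

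- The heat caution is limited to the treatment area.
- The anesthetic exclusion covers drug-reduced sensation at any site, so other causes of sensory loss remain.
- Section 2.6 lets the investigator choose the pad area, but the purpose it gives concerns energy settings and power, with no mention of sensation.
- Section 2.7 names no site for temperature monitoring. Section 4.0 describes temperature sensing through the handpiece connector and mentions none for the neutral connector.
- The pad-capacity requirement in section 4.0 is a real design safeguard, so protection rests only partly on the subject's report. Section 2.14 still warns of pad burns.
- The physical examination in section 2.4 is optional, and the sensory element it lists concerns the extremities.

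**4. What would exclusion cost in numbers?** Inputs: 68 subjects to be enrolled and 43 required (section 2.15.2). Section 2.5 counts a subject as enrolled at consent, so the worst case is that every refusal comes after consent and uses a place. The number of refusals, k, is an assumption (0 to 3), because the documents give no prevalence.

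Share refused = k/68. Places left = 68 − k. Dropout that still leaves 43 = 1 − 43/(68 − k).

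| k | Share refused | Places left | Margin over 43 | Tolerable dropout |
|---|---|---|---|---|
| 0 | 0/68 = 0.0% | 68 | 25 | 1 − 43/68 = 36.8% |
| 1 | 1/68 = 1.5% | 67 | 24 | 1 − 43/67 = 35.8% |
| 2 | 2/68 = 2.9% | 66 | 23 | 1 − 43/66 = 34.8% |
| 3 | 3/68 = 4.4% | 65 | 22 | 1 − 43/65 = 33.8% |

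The margin must also absorb the departures from assumptions that section 2.15.2 mentions.

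**The case against.** The strongest reply is that the protocol already handles this through flagged judgement. The investigator-opinion exclusion is a true exclusion, and the note and the cautions tell the investigator when to consider it. A specific entry for pacemakers and ICDs would ordinarily override the general one, so a switched-off cardiac device needs an unlikely chain: a candidate accepted as healthy, an investigator who sees no significant risk despite the note, and a cardiologist who agrees. For the pad, the investigator may already choose an area with normal sensation. Section 2.7 also makes the Operator's Manual and Clinical Reference Guide part of the study instructions, and these may contain contraindications.

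Some of this stands. The reading of the pacemaker and ICD entries can be disputed. The number of affected subjects may be zero. The absence of pad temperature sensing is inferred from a short specification table. The dropout arithmetic measures the cost of the fix and says nothing about the size of the risk.

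The rest does not remove the gap. The opinion exclusion is discretionary, and a list that says switch off or consult points towards conditional entry. CRT devices lack even the cardiologist step. Freedom to place the pad elsewhere helps only if someone asks about sensation, and the protocol does not require that. If the manuals do contraindicate these subjects, section 2.3 should agree with them.

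**Conclusion.** The concern holds as a minor point of patient safety, with medium confidence. As written, section 2.3 allows entry of subjects with implants in whom the device is untested, and it gives no instruction for heat insensitivity and no cover for the pad site. The existing safeguards reduce both risks without closing either gap.

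The number affected is likely to be very small; the range of 0 to 3 is an assumption. No efficacy result, power or error rate changes. The conclusion rests on the protocol text alone: the Operator's Manual, the Clinical Reference Guide and the consent form were not available and may add rules.

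**What to change.** Move two items to the exclusion list.

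1. **Implants:** exclude any implanted electronic device that emits or receives a signal, including a pacemaker, ICD or CRT device. This replaces the two cautionary entries on implanted electronics; keep the note as the reason.
2. **Heat sensation:** exclude known reduced or absent heat sensation on either flank or at the planned neutral-pad site. Either flank is needed because section 2.16 randomizes the treated side. The pad part does not apply if the pad can go on an area of the back with normal sensation.

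Ask about both in the medical history already taken under section 2.4. No sensation test is needed. Metal implants can remain a caution: that entry already addresses pad placement, the investigator can choose another area, and the subject can still report heat.

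The cost is a protocol amendment with IRB approval (section 21.0), two history questions and the few refusals assumed above. Section 2.11 allows withdrawn subjects to be replaced with approval, which may recover some places. The results would not extend to device carriers or people with reduced heat sensation.

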2.4 Screening

Subjects will be asked questions about their medical history, have their weight recorded, may have a limited physical exam, and their inclusion/exclusion criteria will be verified. Discontinuation of any concomitant medications will be discussed, and pretreatment instructions and post treatment instruction will be reviewed with the subject.

Procedure for the Limited Physical Exam:

If the investigator determines that a limited exam is necessary, the exam will be similar to a basic annual physical exam performed by a primary care doctor to determine general overall health. The limited medical exam may include all or any of the following; vital signs such as blood pressure, heart rate, respiratory rate and body temperature, general appearance, listening to the heart, lungs and abdomen with a stethoscope, head and neck exam, in addition to examining the throat, tonsils, teeth, ears, eyes and nose as well as a neurological exam such as testing muscle strength, reflexes, balance, sensory changes of the extremities and mental state.

The following pre-treatment instructions will be reviewed:

- Shave any dense hair on the area to be treated.
- Do not wear constrictive clothing. Treatment area must be accessible. The back for the neutral pad will also need to be accessed.
- The treatment area must be free of any open lesions or infections.

- For an optimum treatment, keep hydrated by drinking water (at least 8 cups daily) or hydrating fluids, such as Gatorade, and avoid drinking alcohol for 24 hours in advance.

The following post treatment instructions will be reviewed:

- If the skin is slightly pink or red in areas following the treatment, avoid hot water when washing or showering until any erythema (redness) has subsided.
- Soothing creams or moisturizers, such as Aveeno, may be used.
- Gently massage the treated area daily for 5 minutes for the duration of your involvement in the study.
- Use a sun block with UVA and UVB protection with SPF of 30 or greater for 2 – 3 weeks after each treatment to prevent sun damage.
- Maintain the same weight and exercise routine throughout the study.

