2.7 Treatment Procedures

- The Investigator will use the device as described in the TempSure Operator's Manual and Clinical Reference Guide.
- Gel will be applied to the treatment area.
- The TempSure® Firm handpiece (25mm, 30mm, 60mm) to be used and the limits of the area to be treated will be determined by the Investigator and will be used in accordance with the Tempsure Clinical Reference Guide.
- The handpiece will be placed in contact with the skin.
- The entire defined treatment area will then be treated by delivering energy to the skin.
- Parameters may be adjusted throughout the treatment to increase subject comfort.
- Subjects will be asked to report the general level of treatment discomfort/pain on a scale of 0 (none) to 10 (maximum intolerable pain).

- Temperature will be continuously monitored and recorded during treatment.
- Photographs may be taken at any time during treatment to document treatment area and any adverse events, if applicable.
- Subjects may receive up to 5 treatments every 1-2 weeks.
- The additional treatments will follow the same procedure.
- Adverse Events will be documented at all treatment visits.

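### The isotretinoin caution starts its window at six months before treatment, so as written it passes over the most recent users

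*Combined protocol and SAP*

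**What the plan says.** Section 2.3 (Subject Selection Criteria) has inclusion, exclusion and cautionary lists. The cautionary list contains the only mention of isotretinoin in the available text: "The subject has used Accutane (Isotretinoin) six to twelve months prior to treatment, as this can thin the skin and make it brittle". No action is attached to the line.

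Other provisions could reach a recent user, but none names the drug:

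- Section 2.3 excludes on the investigator's judgement: "The subject has any condition or is in a situation which in the investigators opinion may put the subject at significant risk".
- Section 2.4 (Screening) provides that "Subjects will be asked questions about their medical history", and adds that "Discontinuation of any concomitant medications will be discussed".
- Section 2.7 (Treatment Procedures) says of the handpieces and treatment limits that they "will be used in accordance with the Tempsure Clinical Reference Guide". That guide and the operator's manual are attachments that were not available.

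On exposure, section 2.7 states: "Subjects may receive up to 5 treatments every 1-2 weeks". Section 2.14 lists skin burns and scarring among the anticipated side effects.

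**The concern.** The line gives its own reason: the drug leaves skin thin and fragile. On that reason, someone who is taking the drug or stopped last month deserves at least as much caution as someone who took it nine months ago. Yet the wording names two endpoints, and the nearer one is six months back. A site applying it literally would flag the more distant user and pass over the more recent one.

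The stake is small but concerns safety. The device heats skin and underlying tissue, and section 3.3 acknowledges that safety data for this indication are limited. Up to six centers will apply the line and should read it the same way. Nothing here bears on the endpoints or their analysis.

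**Working it through.** The plan states no figure on this point, so there is nothing to reproduce. The check is a reading of the window, followed by simple arithmetic on session timing.

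**1. The window set against possible courses, at treatment 1**

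| Timing of the course | Literal line | Look-back of 12 months to the present |
|---|---|---|
| Ended more than 12 months before | not flagged | not flagged |
| Any use between 12 and 6 months before | flagged | flagged |
| Started less than 6 months before, still ongoing | not flagged | flagged |
| Started and stopped less than 6 months before | not flagged | flagged |

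The two readings differ only in the last two rows.

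**2. How the protocol words other look-backs**

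The pregnancy exclusion in section 2.3 runs plainly up to the present: "has been pregnant in the last 3 months". Section 11.0 is equally clear about the same three-month period. The investigational-product exclusion is looser, "6 months prior to entering this study", but gives a single number and so is still naturally read as a look-back. The isotretinoin line gives two numbers and no word such as *within* or *last*, which invites reading it as an interval.

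**3. Whether another provision closes the gap**

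- Discussing concomitant medications at screening should bring out an ongoing course. It is less likely to bring out one already stopped.
- Taking a medical history may bring out a stopped course, but nothing prompts for this drug.
- The criteria check in section 2.4 refers to the inclusion and exclusion criteria and does not mention the cautionary list.
- Where section 2.3 should list permitted medications, there is only an unfilled template instruction.

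The gap is therefore narrowest for ongoing use and widest for a course both started and stopped within six months.

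**4. If treatment means each session**

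The window then moves forward with each session. Inputs: five sessions, 1 to 2 weeks apart (section 2.7), and an assumed 30.44 days per month. Let *s* be the months from the start of the course to session 1.

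- Span from session 1 to session 5: 4 × 1 = 4 weeks (28 days) up to 4 × 2 = 8 weeks (56 days).
- In months: 28 / 30.44 = 0.92 and 56 / 30.44 = 1.84.
- At session 5 the course began *s* + span months earlier. It is outside the window at all five sessions if *s* + span < 6.
- Weekly sessions: *s* < 6 − 0.92 = 5.08 months. Two-weekly sessions: *s* < 6 − 1.84 = 4.16 months.

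A course begun between that cut-off and six months before session 1 would enter the window only at a later session. With fewer than five sessions the span shortens and the cut-off moves back towards six months. These figures describe the wording only; they measure neither risk nor numbers of subjects.

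**The case against.** The strongest reply is that nobody would read the line strictly. A clinician who sees the reason given will not conclude that use last month needs no caution, and section 2.3 is loosely drafted throughout. Protection also does not rest on this line alone. Subjects must be healthy, the investigator can exclude on judgement, investigators are chosen for experience with this or similar systems (section 3.2), and temperature is monitored continuously during treatment (section 2.7). The manuals that sites must follow may carry their own warning. The line prescribes no action, so a misreading may change nothing.

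Much of this stands. The likely intent is a look-back to the present, the other safeguards are real, and it cannot be determined whether sites lack the warning in practice. These points keep the matter at the lowest level of importance. They do not make the sentence correct, since no other provision in the available text names the drug or corrects the window. Even the charitable reading leaves open whether the outer limit is 6 or 12 months. The session arithmetic is also fairly criticised as adding little: it holds only if treatment means each session and all five are given.

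**Conclusion.** The point holds as a minor wording error in a safety caution. Taken literally, the line omits any isotretinoin course begun less than six months before treatment, which contradicts its own rationale. If the window is applied session by session and all five sessions are given, a course begun less than 5.08 months (weekly sessions) or 4.16 months (two-weekly sessions) before the first session is never flagged.

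The conclusion is limited to the protocol text, because the manuals were not seen. The documents give no figure for isotretinoin use, so the number of subjects affected cannot be stated.

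**What to change.** Replace the timing in the cautionary line of section 2.3 with: *is currently using isotretinoin (Accutane), or has used it at any time in the 12 months before treatment*. Keep the existing reason clause. Twelve months is the protocol's own outer limit; if the sponsor's medical lead prefers six, state that single figure instead.

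The cost is one line in an amendment, with no change to visits, sample size or analysis. The downside is that a few more subjects may be flagged for caution.
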